ICH	International Conference on Harmonisation
ID	Identification
IRB	Institutional Review Board
ISO	International Standards Organization
LAR	Legally Authorized Representative
OR	Operating Room
PMCF	Post-Market Clinical Follow-Up
SAE	Serious Adverse Event

III. Study Synopsis

Title	FastFrame™ External Fixation System Post-Market Clinical Follow-Up Study
Protocol Number	CMU2017-95T
Sponsor	Zimmer Biomet
Legal Manufacturer	Zimmer, Inc.
Study Device(s)	
 • FastFrame External Fixation System – Knee Spanning Kit • FastFrame External Fixation System – Damage Control Kit
Study Objectives/Endpoints	
The objective of this observational, prospective study is to confirm safety and performance of the FastFrame External Fixation System and corresponding instrumentation.
 
 • Primary Endpoint Frequency and incidence of device-related adverse events and device deficiencies before the FastFrame

	
External Fixation System is exchanged by another device (i.e. plates, screws, etc.).
 
 • Secondary Endpoint Adverse events that occur between application of the FastFrame External Fixation System and exchange with another device that do not fall within the primary endpoint.
Indications/Target population	
66 patients in the United States who have undergone fracture stabilization using the FastFrame External Fixation System - Knee Spanning Kit or Damage Control Kit

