Inclusion/Exclusion criteria	
Inclusion Criteria:
 
 • Patient must be 18 years of age or older • Patient must have been treated with either Knee Spanning or Damage Control FastFrame External Fixation System according to the indications stated in this protocol* 
Exclusion Criteria:
 
 • Patient has an active or suspected infection • Conditions that limit the patient's ability and/or willingness to follow instructions during the healing process • Inadequate skin, bone, or neurovascular status • Patient is a prisoner • Patient is pregnant and/or breastfeeding • Patient is a known current alcohol and/or drug abuser in the opinion of the Investigator • Patient has a mental or neurologic condition that will not allow for proper informed consent and/or participation in follow-up program in the opinion of the Investigator 
*EEA Indications (a subset of the cleared US indications): The FastFrame External Fixation System – Knee Spanning Kit is indicated for use in treatment of long bone (distal femur, proximal tibia) fractures. Specifically, the system is intended for temporary stabilization of open or closed fractures about the knee, typically in the context of polytrauma or where open or alternative closed treatment is undesirable or otherwise contraindicated.
 
The FastFrame External Fixation System – Damage Control Kit is indicated for use in treatment of mid-shaft long bone (femur, tibia) fractures. Specifically, the system is intended for temporary stabilization of open or closed fractures of the femur and tibia, typically in the context of polytrauma or where open or alternative closed treatment is undesirable or otherwise contraindicated.

Study Design	Prospective enrollment, prospective follow-up, single cohort study
Clinical Phase	Postmarket
Sample Size	Considering a 95% device success rate (5% device related complications) and a 10% non-inferiority margin, 60 subjects with a follow-up are required. With an estimated lost to follow-up/subject withdrawal rate of 10%, 66 subjects will have to be enrolled.
Length of Study	3 years (2 years of enrollment plus follow-up until exchange with another device) A follow-up visit will be completed at the time of exchange from FastFrame System to another device. Typically, this exchange occurs 2 to 4 weeks after injury.

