Materials and Methods	Device-related complications and device deficiencies will be reported at the baseline/operative and follow-up visits, if applicable. If required, photographs of the study device will be taken to document any loss of stability requiring unplanned adjustment of the study device.
Data Collection	eCRF
Statistical Reporting	Data collected will be summarized and reported to each participating Investigator. Statistical analysis will be conducted by Zimmer Biomet (or Designee).
Scores/Performance Assessments	Device-related complication and device deficiency rates will be recorded
Standards	The PMCF is compliant with the below: 
• ISO 14155:2020 - Clinical investigation of medical devices for human subjects - Good clinical practice.• The Declaration of Helsinki (DoH) - Ethical principles for medical research involving human subjects.• European Regulation (EU) 2017/745• MDCG 2020-10/1• Safety reporting in clinical investigations of medical devices under the Regulation (EU) 2017/745

IV. Data Collection Overview

The following table indicates the necessary CRFs to be completed at each given time point throughout the study. The person responsible for completing each CRF is also listed. Please note the **Site Delegation Log** may list designees for the investigator who are also allowed to complete specific CRFs.

CRF	Baseline/Operative (Day 1)	Follow-Up (Day 14-28)
Informed Consent (ICF)	Patient	
Inclusion/Exclusion Criteria	Investigator	
Demographic Evaluation	Investigator	
Operative Record	Investigator	
Surgical Device	Investigator	
Physician Imaging Assessment	Investigator	Investigator (as applicable)
Physician Follow- Up Assessment		Investigator
Study Completion		Investigator
Adverse Event Report*	Investigator (as applicable)	Investigator (as applicable)
Protocol Deviation	Investigator (as applicable)	Investigator (as applicable)

* If a device-related Adverse Event occurs, supporting documents must be sent to the Sponsor and include the operative report and any relevant imaging

Required for Patient to be considered enrolled in the study

V. Introduction and Purpose

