The management of orthopaedic polytrauma patients has developed greatly since the 1970s, when patients were deemed incapable of undergoing surgery³. In recent years, the use of temporary stabilization of fractures has been used with the goal to decrease operative time³, blood loss³, and the “second hit” inflammatory response from definitive surgical fixation². External fixators, a type of device intended for temporary stabilization, are typically made up of a combination of a frame, clamps, pins, and bars that properly stabilize and support the injured limb¹. In order for this stabilization to occur, the fractured bones are adjusted to reduce the fracture and the bars are connected to maintain the reduction¹. Unlike typical external fixators, the FastFrame External Fixation frames are pre-assembled and are designed for simplicity in the operating room. Each kit includes clamp bodies, pins, and telescoping bars that allow for proper reduction and rigid external fixation. This study will document the clinical outcomes of

trauma patients who require the use of the FastFrame External Fixation System - Knee Spanning and Damage Control kits legally manufactured by Zimmer, Inc.

VI. Study Objectives

The objective of this observational, prospective study is to confirm safety and performance of the FastFrame External Fixation System and corresponding instrumentation. The endpoints are defined to include the following:

Primary Endpoints

- Frequency and incidence of device-related adverse events and device deficiencies before the FastFrame External Fixation System is exchanged by another device (i.e. plates, screws, etc.). Refer to Section XII for additional details related to adverse event classification and device deficiencies.

Examples of device-related adverse events and device deficiencies include:

- Pin breakage and/or loosening requiring surgical intervention (i.e. pin removal or exchange) before planned exchange of the complete frame by another device
- Frame component failure (i.e. loosening, breakage, etc.) leading to clinically unacceptable loss of stability requiring unplanned readjustment or replacement of the frame

Secondary Endpoints

- Adverse events that occur between application of the FastFrame External Fixation System and exchange with another device that do not fall within the primary endpoint. Refer to Section XII for additional details related to adverse event classification.

VII. Study Design and Endpoints

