All surgeries will take place following the standard, approved surgical technique. During the course of the surgery, a **Surgical Device** CRF must be completed documenting the part and lot numbers of the implants. The FDA cleared or other local government regulatory body approved instructions for use and surgical technique must be followed for this product. Please refer to the latest versions of these documents on the Zimmer Biomet website, contact your local Clinical Study Manager, or contact a Zimmer Biomet sales associate for additional details. The following operative data will be collected on the following CRFs:

- **Operative Record**
- **Surgical Device**
- **Protocol Deviation, if applicable**
- **Adverse Event Report, if applicable**
- **Physician Imaging Assessment**
- **Photographs of study device in two (2) planes (A/P and lateral)**

Photographs will be stored in the Subject Binder as part of their casebook. Please write the Subject Case ID Number, Subject Initials, and Date (YYYY-MM-DD) on the photographs. If an adverse event occurs, an **Adverse Event Report** CRF will also be completed. See Management of Incurrent Events for additional details. Reason(s) for study completion must be documented on the **Study Completion** CRF.

Post-Operative Follow-Up Procedure

Post-operative clinical assessment will be conducted at the device exchange follow-up visit after the procedure. The device exchange of a FastFrame External Fixation Kit typically occurs 2-4 weeks after surgery. The following

CRFs will be collected at the follow-up visit when the study device is removed from the subject:

- **Physician Follow-Up Assessment**
- **Protocol Deviation, if applicable**
- **Adverse Event Report, if applicable**
- **Physician Imaging Assessment, if required**
- **Photographs of study device in two (2) planes (A/P and lateral), if required**
- **Study Completion**

Subjects will be followed post-operatively until the FastFrame External Fixation Kit is exchanged with another device or unless the primary endpoint is reached prior. Unless the study is otherwise closed, data will continue to be collected until the subject completes the study per the protocol, voluntarily withdraws from the study, is withdrawn from the study by the Investigator, is lost to follow-up, undergoes revision to remove a study device (does not include device removal as part of standard treatment), or expires.

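### The rules for ending data collection conflict: two of them can stop observation with the frame still on, although both endpoints run to exchange with another device

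*Combined protocol and SAP*

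**What the plan says.** **Endpoint windows.** Section VI defines the primary endpoint as "Frequency and incidence of device-related adverse events and device deficiencies before the FastFrame External Fixation System is exchanged by another device". The secondary endpoint is "Adverse events that occur between application of the FastFrame External Fixation System and exchange with another device that do not fall within the primary endpoint". Both windows close at exchange. The synopsis (Length of Study) agrees: "2 years of enrollment plus follow-up until exchange with another device". Section XI (Study Termination) expects participation to end at the device exchange visit.

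**Examples of primary events.** Section VI gives two: "Pin breakage and/or loosening requiring surgical intervention (i.e. pin removal or exchange) before planned exchange of the complete frame by another device", and frame component failure "leading to clinically unacceptable loss of stability requiring unplanned readjustment or replacement of the frame". A pin exchange or a readjustment can leave the frame in place.

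**Stop rules.**

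- Section X, Post-Operative Follow-Up Procedure, first sentence on follow-up: "Subjects will be followed post-operatively until the FastFrame External Fixation Kit is exchanged with another device or unless the primary endpoint is reached prior".
- Section X, next sentence: data are collected until the subject completes the study, withdraws or is withdrawn, is lost, has a revision to remove a study device, or dies. Reaching the primary endpoint is not listed.
- Section XI, Schedule: when early removal of one or more components is necessary, then after the revision surgery the site completes an Adverse Event report and a Study Completion form that ends the subject's participation.
- Section XI, Study Termination: the exchange visit, with exceptions that include an unplanned revision to remove a study device. Reaching the primary endpoint is not listed.

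The synopsis lists the study devices as the two kits, one of them being the "FastFrame External Fixation System – Damage Control Kit". Section IX lists pins among the contents of a kit. A component is therefore less than a study device.

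**The concern.** A site can follow these rules faithfully and still stop observing a subject before the endpoint window closes. The Section X clause does this after a frame readjustment, and the Section XI Schedule rule does it after a pin removal or exchange. The Section X clause is also undefined for an individual, because the primary endpoint is a frequency and incidence. Each site must decide what it means for one subject to reach it.

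The loss is selective: it falls on the subjects who have already had a device problem. Two outputs are exposed, namely the frequency part of the primary endpoint and the secondary adverse event counts. In a study meant to confirm safety, both would be biased downwards, and sites could differ in how far.

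**Working it through.** **1. The plan's own figure.** Section XV gives an expected success rate of 95%, a margin of 10 points (null 85%), a one-sided exact binomial test at 0.05, and 60 evaluable subjects. With X successes out of 60:

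- P(X ≥ 56 | 0.85) = 0.0424 and P(X ≥ 55 | 0.85) = 0.097, so the rule is at least 56 of 60.
- P(X ≥ 56 | 0.95) = 0.820.

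The plan's approximately 80% power is reproduced.

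**2. Stop after a first primary event.** I take failure to mean at least one primary event. A subject stopped at a first event is already a failure, and later events cannot change that. The alpha of 0.042 and power of 0.82 stand.

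**3. Subjects cut off (upper illustration).** Assume that every first event leaves the frame on and that follow-up stops there. The 5% is the complication rate for comparable devices in Section XV and may not cover device deficiencies.

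- At 5%: 60 × 0.05 = 3 (95% binomial range 0 to 7).
- At the 15% null: 60 × 0.15 = 9 (range 4 to 15).

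**4. Primary events missed.** Assume Poisson events with mean m per subject, where p = 1 − exp(−m), so m = −ln(1 − p). Stopping at the first event records p per subject instead of m. The share missed is 1 − p/m.

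| p | m | all events, 60m | recorded, 60p | missed | share |
|---|---|---|---|---|---|
| 0.05 | 0.0513 | 3.08 | 3 | 0.08 | 2.5% |
| 0.15 | 0.1625 | 9.75 | 9 | 0.75 | 7.7% |

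If half of first events are whole-frame exchanges for another device, nothing further can be missed in those subjects. The shares become 0.0388/3.0388 = 1.3% and 0.3756/9.3756 = 4.0%. Clustering of events within subjects would raise all of these, but the documents give no dispersion. They give no rate for secondary adverse events either, so that loss cannot be sized.

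**5. When the test could move.** This needs a Schedule-rule stop after a removal that is not a primary event, with the subject then scored a success. Let q be the share of subjects so stopped, at a uniformly random time under constant hazard. The observed failure rate is (1 − q)p + q(1 − p/m). At a true failure rate of 15%:

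| q | observed failure rate | chance of passing |
|---|---|---|
| 0 | 0.1500 | 0.042 |
| 1% | 0.1493 | 0.044 |
| 2% | 0.1485 | 0.045 |
| 5% | 0.1464 | 0.049 |
| 10% | 0.1427 | 0.058 |

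The 0.05 level is crossed only at q of about 5.4%. All values of q are assumptions.

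**The case against.** **The Section X clause is partly answered in place.** Its next sentence continues data collection to a list of events that does not include reaching the primary endpoint. Sections IV and X place the Study Completion form at the visit when the device is removed. Section XI requires adverse events to be documented throughout the investigation. This stands as a reason to expect early cut-off under that clause to be uncommon. It does not remove the conflict, and it does not reach the Schedule rule, which orders its own Study Completion form.

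**The Schedule rule is narrower than it first looks.** It covers a necessary early removal, followed by revision surgery and reported as an adverse event. Under Section XII, adverse device effects include those from implantation, malfunction and use error, relatedness extends to the procedure, and unassessable cases default to possible. Most such removals would plausibly be primary events. This stands too.

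**Stronger readings that the documents do not support.** A reader might infer that the primary test is anti-conservative, pointing to 0.058. That figure needs 10% of subjects stopped after non-primary removals, twice the planned complication rate, and all scored as successes. The documents give neither a rate for such removals nor a scoring rule for these subjects. A reader might also infer that an event on one frame ends observation of another in a subject with two. The Schedule rule does speak of the subject, but Section X gives each bilateral procedure its own Case ID and Section XI requires separate forms per device, so most of these data are already separated. With 3 such subjects assumed and independent frames, the expected number of missed first events is 3 × 0.05² = 0.0075 at 5%, and 3 × 0.15² = 0.07 at 15%.

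**Conclusion.** The contradiction is real, and it concerns when endpoint observation ends. Severity is minor to moderate. Following the two early-stop rules as written undercounts event frequency and secondary adverse events in subjects with device problems.

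The size is modest. The figures of 3 of 60 subjects and 2.5% of primary events at a 5% rate (9 of 60 and 7.7% at 15%) are an upper illustration for how often the frame stays on and follow-up stops. They rest on Poisson events without clustering. The unsized part is the secondary adverse events after the stop.

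The sample size and the exact test are not in dispute. The test would be affected only through stops after non-primary removals scored as successes, and the documents do not show that these occur at a rate that matters.

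**What to change.** This concerns data collection only and leaves treatment with the investigator.

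- Reconcile Section X (Post-Operative Follow-Up Procedure) and Section XI (Schedule; Study Termination) to one rule, applied per case or frame. Device events and adverse events are collected until exchange with a device other than FastFrame, or until withdrawal, loss to follow-up or death.
- Delete the Section X clause that ends follow-up when the primary endpoint is reached.
- State that removal or exchange of a component, readjustment of the frame, or replacement by another FastFrame does not by itself trigger the Study Completion form. Replacement needs naming: a rule tied only to removal of the complete frame would still stop collection when a second FastFrame is applied, before exchange with another device.
- In Section XV, use the first event per case for the success rate and count all events to exchange for frequency.

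Alternatively, redefine the primary endpoint as the first event and drop frequency. The secondary endpoint's window would then have to match, and the Schedule rule would still need limiting so that a non-primary removal does not end observation.

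The cost is wording in three places plus one sentence in Section XV. Adverse event collection continues for a few subjects (about 3 of 60 at 5%, if every first event leaves the frame on) to an exchange visit that is already scheduled.

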All components removed outside of standard of care should be promptly returned to Zimmer Biomet for analysis. The Investigator or Designee must notify the Clinical Study Manager prior to the return of any device. Properly prepared components are to be sent to the following address:

Zimmer Biomet
Attention: Product Services Department
[name]
[name] USA

Investigator Withdrawal

The Investigator can choose to withdraw a subject from the study if it is deemed to be in the subject's best interest or the subject does not consent to continue in the study after being informed of changes in the research that might affect them. The reason for the Investigator's withdrawal of the subject must be documented on the **Study Completion** CRF.

Subject Withdrawal

Study subjects may choose to withdraw from the study at any time, for any reason. If possible, a final evaluation will be completed for any subject whom no longer wishes to participate in the study. The reason for the subject withdrawal must be documented on the **Study Completion** CRF.

Lost to Follow-up

Subjects will be considered lost to follow-up after they have missed their follow-up visit and a reasonable number of attempts to locate and evaluate them have failed. All attempts of contact have to be documented on the **Study Completion** CRF and in particular, the reason should be documented. Patients lost to follow-up will not be replaced within the study.

Protocol Deviations

The Investigator should not deviate from the agreed upon protocol unless it is to eliminate hazard to the patient. However, any deviation from the protocol has to be documented on the **Protocol Deviation** CRF along with an explanation for the

deviation and reported to the Sponsor. Each significant deviation will be reported to the IRB, if applicable, within the appropriate deadlines stipulated by the appropriate regulatory authorities. Significant deviations are defined as those impacting or potentially impacting patient safety.

Investigator disqualification criteria leading to exclusion from the clinical study include fraud, misconduct, and serial non-compliance.

Study Termination

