The outcome indicates the subject died as a direct result of the reported adverse event.

XIII. Monitoring

Prior to initiating the clinical study, the Sponsor may conduct a site evaluation visit to ensure the Investigator(s) and study staff understands the study protocol and requirements and have adequate time and resources to implement and conduct the study. Prior to study initiation, the Investigator must have a fully executed CTA, IRB approval of the study protocol, and the study **Informed Consent**.

During the course of the study, the Sponsor will conduct periodic central monitoring and maintain contact with the study staff to monitor compliance and evidence of adverse events in accordance with the Sponsor's policies and procedures. The Sponsor will address any identified non-compliance with the executed CTA, study protocol, and applicable regulatory requirements.

If onsite monitoring visits are deemed appropriate by the Sponsor, the Investigator will permit representatives of the Sponsor's monitoring team to have direct access to inspect all source data/documents, study documents/binders, study subject case report forms, corresponding sections of study subject medical/hospital records, and any other documents relevant to the study. All Sponsor visits will be documented using the **Monitoring Visit Log**.

XIV. Risk Analysis

This PMCF is classified as minimal risk and there are no anticipated risks specific to study participation other than the potential loss of confidentiality. There are no experimental procedures in this study and participation in this study is not anticipated to affect the medical treatment of enrolled subjects.

When used in accordance with product labeling, the risks associated with the use of the FastFrame External Fixation System are similar to those of the historical standard, the XtraFix® External Fixation System by Zimmer, Inc., when used for the same clinical indication or purpose. These risks are either general surgical risks or risks associated with the subject procedure/study device; however, unanticipated adverse events can occur.

XV. Statistical Methods

General Statistical Methods

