Statistical methodology will consist of summarizing collected data descriptively. Categorical data (i.e., gender or race) will be summarized using counts and percentages, and 95% CI, over the time periods of interest. Continuous data, such as age, will be summarized by using means, medians, standard deviation, minimum, maximum, and 95% CI over the time periods of interest. Implant survival will be summarized using a Kaplan-Meier method and presented with rates (as percentages) and confidence intervals.

Sample Size

Calculation of sample size is based on previously published literature involving longitudinal data collection on temporary external fixation. Assuming a power level of 80% and an alpha level of significance of 0.05 ($\alpha = 0.05$), calculations were performed in order to determine the sample size needed for study significance using the following hypothesis test:

The hypothesis will be tested by the exact binomial test:

$$H_0: E_1 - E_0 \leq -\delta E$$

$$H_a: E_1 - E_0 > -\delta E$$

where:

$E_0 = 95\%$, the expected success rate

E_1 = the success rate in the FastFrame System treatment group

$\delta E = 0.10$, non-inferiority margin

In addition, one-sided 95% exact confidence Interval (CI), lower limit of the success rate, will be calculated.

Based on the hypothesis test above, 60 subjects will provide approximately 80% power for the one-sided exact binomial test at 0.05 significant level. The sample size was calculated using SAS for Windows version 9.4.

It was determined that the complication rate of devices comparable to the FastFrame External Fixation System is approximately 5%. Utilizing this figure, the power, and alpha level of significance, a sample size total (without any subjects becoming lost to follow-up) of 60 was obtained. Finally, in order to maintain a sample size large enough for statistical significance an estimated, 90% subject return rate is assumed for the duration of the device exchange follow-up visits. These lost to follow-up patients increase the sample size requirements to 66 subjects (after rounding up).

Visit	Subjects remaining in the study
Baseline	66
Follow-Up	60

XVI. Quality Control & Quality Assurance

The study is conducted in accordance with the Declaration of Helsinki and the ISO 14155:2020 and Regulation (EU) 2017/745.

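### The plan does not seek the primary outcome from records once a subject is lost to follow-up or withdrawn by the investigator, which leaves a test that passes at four failures in 60 open to outcome-related loss.

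*Combined protocol and SAP*

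**What the plan says.** The only follow-up visit is the device exchange itself, typically 2 to 4 weeks after injury or surgery (Section III, Length of Study; Section X, Post-Operative Follow-Up Procedure). The primary endpoint is device-related adverse events and device deficiencies before that exchange (Section VI).

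Four provisions decide what happens when the visit does not take place:

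- **Loss to follow-up (Section XI, Lost to Follow-up).** "Subjects will be considered lost to follow-up after they have missed their follow-up visit" is the first condition. The same sentence adds a second: reasonable attempts to locate and evaluate the subject must also have failed. Lost subjects are not replaced.
- **Investigator withdrawal (Section XI).** "The Investigator can choose to withdraw a subject from the study if it is deemed to be in the" subject's best interest, or if the subject does not agree to go on after being told of changes in the research. Only the reason is recorded. A final evaluation, if possible, is foreseen for subject withdrawal but not here.
- **End of collection (Section X).** Data are collected until one of several exits, among them that the subject "is withdrawn from the study by the Investigator, is lost to follow-up". Section XI, Study Termination, ends participation on similar grounds.
- **Allowance (Section III, Sample Size).** "With an estimated lost to follow-up/subject withdrawal rate of 10%, 66 subjects will have to be enrolled".

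Section VIII places all enrolled eligible subjects in the primary analysis. The sample size counts only those with follow-up, and no rule covers a missing outcome.

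**The concern.** The attempts that precede a classification as lost are attempts to reach and examine the person. They are not attempts to find the outcome. Yet the outcome may exist in writing: exchange to plates or screws is a procedure, the endpoint examples in Section VI involve surgical intervention or unplanned readjustment or replacement of the frame, and Section XI (Retention of Records) already counts hospital records among the study records.

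Investigator withdrawal raises the same issue. Section XIV states that "participation in this study is not anticipated to affect the medical treatment of enrolled subjects", so ending passive recording does not change care, but it can end safety recording while the frame is still on.

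In a single-arm study nothing offsets selective loss. If subjects who leave early fail more often than those who stay, the observed success rate is too high, and the expected number without follow-up is larger than the whole failure allowance of the test.

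**Working it through.** **Inputs.** Section III: "Considering a 95% device success rate (5% device related complications) and a 10% non-inferiority margin, 60 subjects with a follow-up are required". This gives a null success rate of 0.95 − 0.10 = 0.85. Section XV: "60 subjects will provide approximately 80% power for the one-sided exact binomial test at 0.05 significant level". Enrolment is 66, so the planned number without follow-up is 66 − 60 = 6.

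**Step 1: the plan's own figure.** With X failures, the test passes if P(X or fewer failures | n, failure rate 0.15) ≤ 0.05.

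| Failures / n | p-value | One-sided 95% exact lower limit | Result |
|---|---|---|---|
| 3/60 | 0.015 | 87.6% | pass |
| 4/60 | 0.042 | 85.4% | pass |
| 5/60 | 0.097 | 83.3% | no pass |

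Power is P(4 or fewer of 60 | failure rate 0.05) = 82.0%. The stated figure of about 80% is reproduced.

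**Step 2: how few unseen failures change the result.** With all 66 outcomes known:

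| Failures / n | p-value | Lower limit | Result |
|---|---|---|---|
| 4/66 | 0.023 | 86.7% | pass |
| 5/66 | 0.056 | 84.7% | no pass |

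- 4 failures seen in 60: one failure among the six unseen reverses the result. At the plan's own 5% rate, the chance of at least one is 1 − 0.95^6 = 26.5%.
- 3 failures seen in 60: two unseen failures reverse it. The chance of at least two among six is 3% if they fail at 5%, 22% at 15% and 58% at 30%. The last two rates are assumptions.

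**Step 3: false-pass probability.** Let the true failure rate be 15% over all 66, the edge of the null hypothesis, so 0.15 × 66 = 9.9 expected failures. Let the six lost subjects fail at rate q (assumed). Those seen then fail at (9.9 − 6q)/60, and the false-pass probability is P(4 or fewer of 60) at that rate.

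| Lost subjects | Failure rate in those seen | False pass |
|---|---|---|
| six at 15% (loss unrelated to outcome) | (9.9 − 0.9)/60 = 15.0% | 4.2% |
| six at 30% | (9.9 − 1.8)/60 = 13.5% | 7.9% |
| six at 40% | (9.9 − 2.4)/60 = 12.5% | 11.6% |
| six at 50% | (9.9 − 3.0)/60 = 11.5% | 16.6% |
| three at 40%, three at 15% | (9.9 − 1.2 − 0.45)/60 = 13.75% | 7.1% |

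**Step 4: effect of full recovery.** With 66 outcomes the limit is still 4 failures. Exact alpha falls from 4.2% to 2.3% and power from 82.0% to 76.6%.

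**The case against.** Several stronger readings are tempting, and the documents do not support them.

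- *A missed visit alone ends collection.* It does not; contact attempts must also fail, and they must be documented.
- *At most six outcomes are at risk, and all six could be recovered.* Six is a planning allowance, not a cap. It also covers subject withdrawals, and those who withdraw consent are outside any remedy. The number that can be recovered is unknown and, at the planned rate, probably below six. The last row in Step 3 shows the smaller effect.
- *Events that prompt withdrawal vanish.* Section XI requires adverse events to be recorded with their relationship to the device, and early component removal to be reported as an adverse event. Section XII has an outcome category for study withdrawal. What can be lost are events after exit, or events the site never learns of.
- *Subjects who miss the visit have had the frame removed elsewhere.* No section says so, nor that outside operative notes can be obtained. Both are inferences.
- *The best-interest ground protects nobody and should go.* Section XIV names loss of confidentiality as a risk of participation, and further record searches bear on it. The ground may stay; the issue is only that it should not automatically end passive recording.
- *The consent form lacks a record release.* The consent pages are not available for review, so this cannot be said.

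It is also fair to object that the case for bias rests on assumed failure rates. At the plan's 5% rate, two or more failures among six have only a 3% chance. If lost subjects fail less often than the rest, the bias runs the other way.

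What stands is the gap itself: no provision seeks the outcome from records at the point where the plan stops collecting.

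**Conclusion.** The point holds as a gap in outcome collection, with a possible upward bias in the success rate. The plan's margin is thin: it passes at 4 of 60 and not at 5, with about six subjects expected to be without follow-up. Under the assumed failure rates of 30% to 50% in six lost subjects, the false-pass probability is 7.9% to 16.6%, against 4.2%; with three such subjects at 40% it is 7.1%. These sizes assume that lost subjects are left out of the test, that they fail more often than the others, and that the true overall failure rate is 15%. The documents establish neither the direction nor the strength of the link between loss and outcome.

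A reader might infer that recovering outcomes would also raise power. It would not; the argument is about bias alone.

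**What to change.** In Section X (Post-Operative Follow-Up Procedure) and Section XI (Lost to Follow-up, Investigator Withdrawal), with Study Termination aligned:

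1. State that a missed visit or an investigator withdrawal ends study visits but not passive outcome collection.
2. Where consent allows, and unless the subject withdraws or declines consent to continue, have the site record the exchange date, any unplanned intervention, and device-related events and deficiencies up to exchange. The source is its own chart or an outside operative note that can be obtained.
3. Class a subject as lost only after that attempt has failed.
4. Check that the consent form covers this use of records.

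The cost is protocol wording and a few record requests, at most about six at the planned rate, with no added visit or procedure. Outside records may not always be obtainable, so some outcomes will stay missing. The sponsor should also accept in advance that full recovery of all 66 outcomes leaves the limit at 4 failures, with exact alpha 2.3% and power 76.6%.
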